Appendix 1: Development of gene therapy for inherited skin diseases

Method	Target gene	Condition	Target cell	Comments	Reference
Self-inactivating lentiviral vector	COL7A1	Recessive dystrophic EB	In vivo	In vivo inoculation of skin equivalents grafted onto mice, C7 expression up to 3 months	1
Self-inactivating lentiviral vector	COL7A1	Recessive dystrophic EB	Fibroblast	Gene corrected fibroblasts injected into murine skin able to produce C7 at basement membrane zone	2
Gamma retroviral vector	COL7A1	Recessive dystrophic EB	Keratinocyte	Construction of skin equivalents using classical retroviral gene transfer; transduction efficiency 40%	3
Self-inactivating gamma retroviral vector	COL7A1	Recessive dystrophic EB	Keratinocyte + Fibroblast	Generation of human skin equivalents showing in vivo functional correction of phenotype; C7 expression of recombinant C7 ranging between 30-80% keratinocytes and 40-70% fibroblasts	4
Retroviral vector	COL7A1	Recessive dystrophic EB	Keratinocyte	Genetic correction of both dog RDEB and human primary RDEB cells	5
φC31 integrase based plasmid	COL7A1	Recessive dystrophic EB	Keratinocyte	Nonviral approach into primary RDEB cells; regenerated skin (40% efficiency); stable correction required short-term drug selection and enrichment	6
3' pre-transplicing molecule	COL7A1	Recessive dystrophic EB	Keratinocyte	Trans-splicing used to reduce size of COL7A1 transcript and therefore risk of genetic rearrangement	7
φC31 integrase based	LAMB3	Junctional EB	Keratinocyte	Nonviral approach showing corrected hemidesmosome formation in JEB primary cells	8

plasmid					
Transposase (sleeping beauty)	LAMB3	Junctional EB	Keratinocyte	Sleeping beauty transposable element used to integrate LAMB3 cDNA into epidermal cells in 6 JEB patient primary cells; transfected cells enriched using drug selection.	9
PAC (P1-based artificial chromosome clone)	COL7A1	Recessive dystrophic EB	Keratinocyte	Gene transfer using micro-injection of entire human locus COL7A1 in a P1 derived artificial chromosome	10
TALEN gene editing	COL7A1	Recessive dystrophic EB	Fibroblasts	Transcription activator-like endonucleases (TALEN) gene editing of RDEB fibroblasts subsequently reprogrammed into iPS cells (induced pluripotent stem cells)	11
Gamma retroviral vector	COL17A1	Junctional EB	Keratinocyte	Restoration of full-length BP180 protein expression in primary keratinocytes then used to regenerate human skin on immunodeficient mice	12
Gamma retroviral vector	LAMB3	Junctional EB	Keratinocyte	Only case of successful gene transfer in an inherited skin disorder in an adult patient with non-herlitz junctional EB; restored phenotype and laminin 332 expression 7 years post graft	13
Self-inactivating lentiviral vector	LAMB3	Junctional EB	Keratinocyte	Pre-clinical study using potentially safer LV	14
Gamma retroviral vector	XPC	Xeroderma pigmentosum	Keratinocyte + Fibroblast	Functional in vitro correction of XPC keratinocytes	15
Adenoviral vector	XPA	Xeroderma pigmentosum	In vivo	In vivo inoculation of recombinant AV vector in UV irradiated murine skin	16
Self-inactivating lentiviral vector	XPA/ XPC/ XPD	Xeroderma pigmentosum	Fibroblast	Efficient SIN LV vector able to correct cellular phenotype in XP	17
Gamma retroviral vector	XPC	Xeroderma pigmentosum	Keratinocyte	MLV derived vector able to transduce primary cells and maintain XPC expression in up to 130 population doublings	18

TALEN gene editing	XPC	Xeroderma pigmentosum	Fibroblast cell line	Successful targeted gene correction of XPC cell line	19
Self-inactivating lentiviral vector	SPINK5	Netherton syndrome	Keratinocyte	Pre-clinical work demonstrating full length LEKTI expression in organotypic cultures grafted onto mice. Currently recruiting for phase I clinical trial	20
Retroviral vector	STS	X-linked ichthyosis	Keratinocyte	Restoration of enzymatic activity in cultured primary keratinocytes deficient in steroid sulfatase	21
siRNA	KRT5	EB Simplex	Keratinocyte	Pre-clinical study, specific knockdown of mutant keratin 5	22
siRNA	KRT6A	Pachyonychia congenital	Keratinocyte	Phase 1b trial injecting TD101 siRNA locally for plantar keratoderma in PC	23
Direct injection of plasmid	TGM1	Lamellar Ichthyosis	Keratinocyte	Non-uniform restoration of gene expression on regenerated LI skin	24

ABBREVIATIONS: AV, adenoviral; C7, type VII collagen; EB, epidermolysis bullosa; LI, lamellar ichthyosis; LV, lentiviral; PC, pachyonychia congenita; RDEB, recessive dystrophic epidermolysis bullosa; SIN, self-inactivating vectors.

Fibroblast	Prospective placebo controlled Phase III trial	Facial Contour deformities	215	Intradermal cultured autologous fibroblasts	Most significant difference evident in acne scars; continued response rates up to 12 months post treatment	2
Fibroblast	Interventional non-blinded prospective study	Adult RDEB	5	Intradermal injection allogeneic cultured fibroblasts; intact skin	↑COL7A1 and C7 for 3 months; can remain raised for up to 9 months	3, 4
Fibroblast	Phase II placebo controlled double blind RCT	Adult RDEB	5	Intradermal cultured allogeneic fibroblasts	No significant difference between placebo; improvement in QOL	5
Fibroblast	Interventional	Ageing skin	5	Intradermal cultured	Benefits limited to slight reduction	6

	non-blinded study			autologous fibroblasts	in skin fragility	
Fibroblast	Phase II open label dose escalation pilot study	Ageing skin	10	Intradermal cultured allogeneic fibroblasts	Slight reduction in nasolabial crease	7
Fibroblast	Single centre interventional study	Ageing skin and scars	20	Intradermal cultured autologous fibroblasts	Variable improvement at 6 months	8
Keratinocyt	Phase II placebo controlled double blind RCT	Chronic Venous Ulcers	228	Spray allogeneic neonatal keratinocyte and fibroblast cell applied therapy	Greater mean reduction of wound size compared with placebo	9
Fibroblast	Prospective interventional study	Burns (third degree)	14	Allogeneic fibroblasts on meshed split thickness skin grafts	Improved healing time and hypertrophic scar formation compared with conventional method	10
Fibroblast	Multicentre double blind placebo controlled Phase II RCT	Ageing skin	372	Intradermal cultured autologous fibroblasts	Moderate improvement in nasolabial fold wrinkles compared to placebo, only 1 point subjective difference	11
Cultured dermal substitute						
CDS	Prospective interventional study	RDEB	3	Allogeneic cultured dermal substitute using cryopreserved normal human	++Granulation found on wound surface within 1 week; epithelialisation at margins of ulcer at 4 weeks	12

				fibroblasts on matrix of hyaluronic acid and Atelo-collagen		
CDS	Case report	Digital gangrene associated with hypereosinophilic syndrome	1	Allogeneic cultured dermal substitute using cryopreserved normal human fibroblasts on matrix of hyaluronic acid and Atelo-collagen; replaced every 3 days for 5 weeks	Pain reduction at site; healthy granulation tissue during treatment and so replaced with split skin graft	13
CDS	Prospective interventional study	Full thickness skin defects following tumour resection	12	Allogeneic cultured dermal substitute using cryopreserved normal human fibroblasts on matrix of hyaluronic acid and Atelo-collagen	9/10 patients developed healthy granulation tissue allowing split skin graft; Others showed rapid re- epithelialisation	14
CDS	Case report	Chronic venous ulcer	1	Allogeneic cultured dermal substitute using cryopreserved normal human fibroblasts on matrix of hyaluronic acid and Atelo-collagen	Granulation tissue within 2 weeks; completely healed by 9 weeks	15

CDS	Multi-centre prospective interventional study	Chronic venous and arterial ulcer	13	Allogeneic cultured dermal substitute using cryopreserved normal human fibroblasts on matrix of hyaluronic acid and Atelo-collagen	9/13 cases (arterial + venous) healed well, one complicated by local infection; larger ulcers still required grafting	16
CDS	Case report	Ulcer associated with Anti-Phospholipid syndrome + stasis dermatitis	1	Allogeneic cultured dermal substitute using cryopreserved normal human fibroblasts on matrix of hyaluronic acid and Atelo-collagen; replaced every week	All ulcers healed within 4 weeks	17
CDS	Prospective interventional study	Intractable ulcers lower leg	5	Allogeneic cultured dermal substitute using cryopreserved normal human fibroblasts on matrix of hyaluronic acid and Atelo-collagen	Wound size decreased in all cases (33% reduction in 7 ulcers, complete resurfacing in 2 cases); no control comparator	18
CDS	Prospective interventional study	Wound donor site following skin graft	14	Comparitive between fresh and cryopreserved human fibroblasts in allogeneic cultured dermal	No difference noted in re-epithelialisation between the preparation methods	19

				substitute		
CDS	Prospective, open label proof of concept clinical trial	Diabetic foot ulcer	5	Autologous fibroblast seeded artificial dermis using animal product free serum	3/5 complete wound healing within 12 weeks; no deleterious effects using animal free serum	20

1.1 Trial objectives

1.1.1 Primary objective

To evaluate the safety of intradermal injections of SIN LV-mediated *COL7A1* gene-modified autologous fibroblasts in adults with recessive dystrophic epidermolysis bullosa (RDEB).

1.1.2 Secondary objectives

- i. To evaluate the potential efficacy of intradermal injections of SIN LV-mediated *COL7A1* gene-modified autologous fibroblasts in adults with RDEB at week (W) 2, month (M) 3 and 12 after the IMP injections.
- ii. To screen for immune response against the recombinant C7 at W2, M1, M3, M6 and M12 after the IMP injections compared to baseline.

1.2 Trial design

This is a prospective phase 1, non-randomised, open label, single-centre, proof-of-concept study.

Each study participant will receive three intradermal injections of *ex vivo* transduced autologous fibroblasts expressing codon-optimised *COL7A1* as the IMP on Day 0 only. Each injection of the IMP containing $0.8\text{--}1.2 \times 10^6$ cells suspended in 0.25ml of 0.9% saline, will be administered intra-dermally into 1cm^2 area of intact skin (x3). Participants will be followed up with study interventions for a 12-month period at various time points as outlined in the trial timeline (Figure 1). All follow-ups, where possible, will be co-ordinated to try to coincide with the individuals' routine clinic reviews.

Each subject will undergo an initial screening including a physical examination and assessment of disease severity. Blood analyses and skin biopsies will be performed at various time points as per the monitoring schedule (Table 1 and Figure 1). The second participant will be treated only if there is no safety concern 4 weeks after the first participant's IMP injections. All patients with RDEB are followed up on a lifelong basis, and it will therefore be possible to capture long-term possible adverse effects related to the IMP.

1.3 Trial timeline

[figure not shown]

Figure 1: LENTICOL-F trial timeline.

*Each injection consists of 0.8–1.2 million cells suspended in 0.25ml of 0.9% saline. Each of three syringes containing the IMP will be administered over 1 cm² area of intact skin. . Virology tests done at V1A & V1B = HIV, HepBsAg, HepBcAb, HepC IgG, HTLV 1&2 and Treponema pallidum serology; Skin procurement and biopsy at V1B = 2 to 3 biopsies (one 6mm procurement for tissue culture for IMP production; and one to two 4mm for C7IF, TEM, qPCR and histology); Skin biopsy @ W2, M3 and M12 = Two 6-8mm biopsies for C7 IF, TEM, qPCR and histology (one from injected site and one from non-injected site). All skin biopsies will be archived for integration site analyses in the rare event of clinically indicated serious adverse events. Pregnancy tests at V1A, V1B and V2: if serum is not obtainable, urine pregnancy test may be performed instead. Historical samples/ results may be used for C7 ELISA & IIF, ELISPOT, C7 IF microscopy & TEM and virology tests.

NB: If W2 and M3 skin biopsy results are negative then M12 biopsy may not be performed. Abbreviations: BEBS score=Birmingham Epidermolysis Bullosa Severity Score; IMP=Investigational medicinal product.

1.4 Method of allocation of groups / randomisation procedure

This is a phase 1, non-randomised, single group, proof-of-concept study. All participants will receive the IMP. Therefore method of allocation to groups and randomisation procedure are not applicable.

1.5 Dosing regimen

Each trial participant will receive three intradermal injections of gene-modified autologous fibroblasts on Day 0. Each 1cm² of intact skin will be injected with 0.8–1.2x10⁶ cells/ 0.25ml of normal saline. Once all 3 syringes are received, they will be injected over 3x1cm² areas.

1.6 Visit schedule

Subjects will be required to visit the clinic 10 times in 12 months. The screening assessment visit (V1A) will be conducted up to 6 months prior to D0 – the day of the IMP injections. The timings of the subsequent visits will be relative to D0 (V2) (Table 1). Timing of screening, treatment and follow-up visits are summarised in the trial flowchart and monitoring schedule.

The end of the trial will be defined as the final study participant's last scheduled follow-up visit according to the protocol, which will be the 12 month follow-up visit after the intradermal injections of the IMP of the last subject entering the trial.

1.7 Procedures by visit

Visit number	V1A	V1B	V2	V3	V4	V5	V6	V7	V8	V9
Timeline of each visit relative to the day of gene-modified fibroblast injections (D0)	Up to 6M prior to D0	At least 6W prior to D0	D0	W1 (±3D)	W2 (±3D)	W4 (±14D)	M3 (±1M)	M6 (±1M)	M9 (±1M)	M12 (±1M)
Approximate duration of each visit (hours)	2	2	1.5	1.5	2	1.5	2	1.5	1.5	2
Informed consent	X									
Inclusion / exclusion	X	X								
Demographics	X									
Medical history	X									
Vital signs	X	X	X	X	X	X	X	X	X	X
Physical examination	X	X	X	X	X	X	X	X	X	X
Serum pregnancy test for female participants with child-bearing potential (if serum is not obtainable, urine pregnancy test may be used)	X	X	X							
^a BEBS Score	X				X		X			X
^b Clinical photography	X	X	X	X	X	X	X	X	X	X
Blood samples	^c Basic bloods		X	X	X	X	X	X		X
	^d Virology		X	X						

Visit number		V1A	V1B	V2	V3	V4	V5	V6	V7	V8	V9
Timeline of each visit relative to the day of gene-modified fibroblast injections (D0)		Up to 6M prior to D0	At least 6W prior to D0	D0	W1 (±3D)	W2 (±3D)	W4 (±14D)	M3 (±1M)	M6 (±1M)	M9 (±1M)	M12 (±1M)
	C7 ELISA & IIF	X				X	X	X	X		X
	ELISPOT			X			X		X		X
	^e RCL	X				X	X	X			X
Skin biopsies	C7 IF microscopy & TEM		X			X		X			X
	^f qPCR		X			X		X			X
	^g Integration site analysis		X			X		X			X
Skin procurement (1x6mm)	Tissue culture for IMP production		X								
^h Intradermal injections of IMP				X							
Adverse event(s) assessment			X	X	X	X	X	X	X	X	
Concomitant medications assessment			X	X	X	X	X	X	X	X	

Table 1: LENTICOL-F trial flowchart with details of interventions at each visit.

Abbreviations: V=Visit; D=Day; W=Week; M=Month.

Consent will be obtained at each visit. On Day 0, your vital signs will be monitored every 15mins for 30mins after the gene-modified fibroblast injections. There will be one-off readings of the vital signs on the rest of the other visits during the study. Historical samples/ results may be used for C7 ELISA & IIF, ELISPOT, C7 IF microscopy & TEM. Historical virology results performed within the last 3 months may be used. NB: If W2 and M3 skin biopsy results are negative then M12 biopsy may not be performed.

^aBirmingham Epidermolysis Bullosa Severity Score;

^bClinical photography of potential injection sites over an area of the intact skin will be taken at screening on visit 1, post-IMP injections on visit 2 and at each visit thereafter;

^cIncludes FBC, U&Es, LFTs, ESR and CRP;

^dIncludes HIV, HepBcAb, HepBsAg, HepC IgG, HTLV 1&2 and Treponema pallidum serology;

^eBlood samples will be archived for replication-competent lentivirus (RCL) - may be archived for at least 15 years and analysed in the event of relevant serious adverse reactions (SAEs) as clinically indicated;

^fVector copy number and *COL7A1* gene expression will be measured using quantitative polymerase chain reaction (qPCR) and some skin samples retained for integration site analysis in the event of clinically indicated SAEs;

^gDNA will be extracted from part of the skin biopsy and archived for integration site analysis in the event of relevant adverse reactions as clinically indicated;

^hEach of 3 intradermal injections of IMP (*COL7A1* gene-modified autologous fibroblasts) will be administered to 1cm² of intact skin

1.8 Long-term follow-up

Patients with RDEB are regularly reviewed, often for life, by the consultant Dermatologists in the multi-disciplinary setting at the regular epidermolysis bullosa (EB) clinics at GSTT, providing opportunities for detection of late adverse events. Once these studies are officially closed, serious events related to the IMP (SARs and SUSARs) will continue to be reported to the MHRA and London – West London & Gene Therapy Advisory Committee (GTAC) in the same way as during the study.

1.9 Selection of participants

The patient population is under the care of the specialist EB team at St John's Institute of Dermatology, GSTT. As a tertiary care centre, patients may have been referred from other regional district hospitals in the first instance. Potential study subjects will be identified from the National EB database that includes patients from both GSTT and nationally and an initial approach made by members of the clinical team. Potential participants may also be recruited from Patient Identification Centres. Study information sheets will be provided and individuals interested will be invited for further consultation and screening, assessed for eligibility, and consented as necessary. All individuals invited to participate in the study will have a minimum of 24 hours to make their decision.

1.10 Inclusion criteria

1. Clinical and genetic diagnosis of RDEB with confirmed bi-allelic *COL7A1* mutations.
2. A reduced number or morphologically abnormal anchoring fibrils confirmed by TEM.
3. At least 5x3cm of intact skin on the trunk and/or extremities that is suitable for cell injections.
4. Able to undergo local anaesthesia.
5. Subjects aged ≥ 17 years and able to give informed consent prior to the first study intervention.

1.11 Exclusion criteria

1. Subjects who received other investigational medicinal products within 6 months prior to enrolment into this study.
2. Past medical history of biopsy proven skin malignancy.
3. Subjects who have received immunotherapy including oral corticosteroids (Prednisolone $>1\text{mg/kg}$) for more than one week (intranasal and topical

preparations are permitted) or chemotherapy within 60 days of enrolment into this study.

4. Known allergy to any of the constituents of the investigational medicinal product (IMP).
5. Subjects with **BOTH**:
 - i. positive serum antibodies to C7 confirmed by ELISA **and**
 - ii. positive IIF with binding to the base of salt split skin.
6. Subjects with positive results for HIV, Hepatitis B, Hepatitis C, HTLV or Syphilis.
7. Subjects who are pregnant or of child-bearing potential who are neither abstinent nor practising an acceptable means of contraception when this is in line with the usual and preferred lifestyle of the subject, as determined by the Investigator, for 12 months after the cell injections.

1.12 Outcome measures

1.12.1 Primary outcome measures

Adverse events (AEs), Serious Adverse Events (SAEs), Adverse Reactions (ARs) and Serious Adverse Reactions (SARs) at each visit after screening over a 12-month follow-up period.

1.12.2 Secondary outcome measures

- Skin biopsy analysis of treated skin at W2, M3 and M12 compared to untreated skin:
 - i. C7 protein expression by direct immunofluorescence microscopy (DIF)
 - a. C7 IF microscopy
 - b. C7 immunofluorescence intensity
 - ii. Morphology of anchoring fibrils at the dermal-epidermal junction (DEJ) by transmission electron microscopy (TEM)
 - a. Number of anchoring fibrils
 - iii. Vector copy number by quantitative polymerase chain reaction (qPCR)
- Serum analysis post-injections compared to baseline for:

- iv. Detection of anti-C7 antibodies by enzyme-linked immunosorbent assay (ELISA) (against NC1 and NC2 domains of C7) and indirect immunofluorescence (IIF) at W2, M1, M3, M6 and M12:
 - a. C7 ELISA - positive or negative
 - b. C7 ELISA value
 - c. IIF – positive or negative
- v. Detection of T-cell responses to the full length C7 by enzyme-linked immunosorbent spot (ELISPOT) assay at M1, M6 and M12 post-injections.
 - a. C7 ELISPOT - positive or negative
 - b. C7 ELISPOT value

1.13 Adverse events

Adverse events and concomitant medications will be reviewed at every visit after V1A. Clinical photographs will be taken at each visit in order to monitor changes in the injection sites especially with regards to any suspicious lesions or adverse reactions locally. If suspicious lesions are detected then, the participant will be immediately assessed and managed by a consultant dermatologist and if found malignant then, the lesion will be excised as per GSTT guidelines. Physical examination and vital signs will be performed at every visit in order to assess any potential systemic adverse effects and treated as appropriate as per GSTT guidelines.

The Medicines for Human Use (Clinical Trials) Regulations 2004 and Amended Regulations 2006 gives the following definitions:

Adverse Event (AE): Any untoward medical occurrence in a subject to whom a medicinal product has been administered including occurrences which are not necessarily caused by or related to that product.

Adverse Reaction (AR): Any untoward and unintended response in a subject to an investigational medicinal product which is related to any dose administered to that subject.

Unexpected Adverse Reaction (UAR): An adverse reaction the nature and severity of which is not consistent with the information about the medicinal product in question set out in the Investigator's Brochure (IB) relating to the trial in question (for any other investigational product).

Serious Adverse Event (SAE), Serious Adverse Reaction (SAR) or Unexpected Serious Adverse Reaction (USAR): Any adverse event, adverse reaction or unexpected adverse reaction, respectively, that

- Results in death;
- Is life-threatening;

- Required hospitalisation or prolongation of existing hospitalisation;
- Results in persistent or significant disability or incapacity;
- Consists of a congenital anomaly or birth defect.

Suspected Unexpected Serious Adverse Reaction (SUSAR): Is defined as a serious adverse drug reaction, the nature and severity of which is not consistent with the information about the medicinal product in question set out in the IB relating to the trial in question, and which results in any of the outcomes set above.

Important Medical Events (IME) & Pregnancy: Although not a serious adverse event, any unplanned pregnancy will also be reported via the SAE reporting system (please see protocol version 4.0, section 9.4 for more details).

- Important medical events that may not be immediately life-threatening or result in death or hospitalisation but may jeopardise the patient or may require intervention to prevent one of the other outcomes listed in the definition above should also be considered serious.

1.13.1 Reporting responsibilities

Please see protocol version 4.0, section 9.4 for detailed reporting responsibilities.

Adverse Events and Serious Adverse Events that do not require reporting

The following will not require reporting although will be documented on the eCRF and will be included in the primary outcome.

Adverse event as a result of venesection and cannulation include:

- i) Mild bruising at site of needle puncture

Adverse event as a result of the skin biopsy include:

- i) Mild bruising at the site of the skin biopsy
- ii) Cutaneous skin infection requiring oral course of antibiotics
A small scar will result after each skin biopsy, resembling an old chickenpox scar.

All hospitalisations which are expected to take place as a result of disease progression including any planned elective surgeries will not be documented on the eCRF and will not be reported at the interim and the end-of-trial safety data analysis however they will be documented in the patient notes. This may include but not limited to:

- Skin
 - Skin infection
 - Review of a wound
 - Skin blisters/ erosions as part of EB wound
- Teeth

- Dental extractions/ abscess
- Hand
 - Hand surgery
 - De-gloving injury
 - Occupational Therapy review and splints
- Transfusions
- Overnight hospital stay for reviews
- Blood monitoring, routine blood tests
- Corneal abrasions
- Eye Infections
- Chronic eye problems due to EB
- Gastrointestinal problems
 - Dysphagia, oesophageal stricture and dilation
 - Gastrostomy insertion, leakage or blockage/ jejunal tube insertion leakage/ blockage
 - Regurgitation or vomiting as a result of oesophageal blisters/ stricture
 - NG tube insertion
 - Constipation
- Vertebral or other fractures
- IV bisphosphonates
- IV iron infusion
- Contractures requiring physiotherapy
- Hydrotherapy
- ENT
 - Tonsillitis
 - Otitis externa
 - Otitis media
- Pain
 - pain assessment for acute or chronic pain
 - pain from ongoing EB wounds
- Accidental injuries causing minor skin wounds

Thus, any hospitalisation that is not associated with the IMP will not be reported, unless the IMP results in a prolongation of existing hospitalisation. Unscheduled and/or emergency hospitalisations that are not expected due to the natural course of the disease will be reported via the sponsor's normal serious adverse event (SAE) reporting practice. AEs will be reviewed at each visit both from the patient's report as well as documentation from medical notes.

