8.1 Primary efficacy parameters

The primary efficacy of this phase 1 trial will be based on the safety of the administration of IMP in adults with RDEB, as analysed according to the incidence of Adverse events (AEs), Serious Adverse Events (SAEs), Adverse Reactions (ARs) and Serious Adverse Reactions (SARs) at each visit after screening over a 12-month follow-up period.

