- The CI and KHP-CTO (on behalf of the co-sponsors), will submit a Development Safety Update Report (DSUR) relating to this trial IMP, to the MHRA and REC annually.

9.5 Adverse Events (AEs) and Serious Adverse Events (SAEs) that do not require reporting

The following will not require reporting although will be documented on the eCRF.

Adverse event as a result of venesection and cannulation include:

- i) Mild bruising at site of needle puncture

Adverse event as a result of the skin biopsy include:

- i) Mild bruising at the site of the skin biopsy
- ii) Cutaneous skin infection requiring oral course of antibiotics

A small scar will result after each skin biopsy, resembling an old chickenpox scar.

All hospitalisations which are expected to take place as a result of disease progression including any planned elective surgeries will not be reported at the interim and the

end-of-trial safety data analysis but will be documented in the patient notes. This may include but not limited to:

- Skin
 - Skin infection
 - Review of a wound
 - Skin blisters/ erosions as part of EB wound
- Teeth
 - Dental extractions/ abscess
- Hand
 - Hand surgery
 - De-gloving injury
 - Occupational Therapy review and splints
- Transfusions
- Overnight hospital stay for reviews
- Blood monitoring, routine blood tests
- Corneal abrasions
- Eye Infections
- Chronic eye problems due to EB
- Gastrointestinal problems
 - Dysphagia, oesophageal stricture and dilation
 - Gastrostomy insertion, leakage or blockage/ jejunal tube insertion leakage/ blockage
 - Regurgitation or vomiting as a result of oesophageal blisters/ stricture
 - NG tube insertion
 - Constipation
- Vertebral or other fractures
- IV bisphosphonates

- IV iron infusion
- Contractures requiring physiotherapy
- Hydrotherapy
- ENT
 - Tonsillitis
 - Otitis externa
 - Otitis media
- Pain
 - pain assessment for acute or chronic pain
 - pain from ongoing EB wounds
- Accidental injuries causing minor skin wounds

Thus, any hospitalisation that is not associated with the IMP will not be reported, unless the IMP results in a prolongation of existing hospitalisation. Unscheduled and/or emergency hospitalisations that are not expected due to the natural course of the disease will be reported via the sponsor's normal serious adverse event (SAE) reporting practice. AEs will be reviewed at each visit both from the patient's report as well as documentation from medical notes.

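### SAP 1.13.1 keeps expected disease-progression hospitalisations off the eCRF and out of both safety analyses, so the tabulated SAE count can only equal or fall below the count the plan defines

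*SAP*

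**What the plan says.** **Primary outcome and definitions.** SAP 1.12.1 makes AEs, SAEs, ARs and SARs over 12 months the primary outcome. SAP 1.13 defines an AE without regard to whether the product caused it. It makes an AE serious if, among other criteria, it required or prolonged hospitalisation. Neither section excepts disease progression. Protocol 8.1 bases the assessment on the incidence of these events. SAP 2.5 promises total counts, the number of patients with at least one event of each type, and a listing of all adverse events (Tables 6 and 7).

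**The hospitalisation rule in the SAP.** SAP 1.13.1 says that hospitalisations expected from disease progression, planned elective surgery included, "will not be documented on the eCRF and will not be reported at the interim and the end-of-trial safety data analysis". They are kept in the patient notes. An open-ended list of examples follows.

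**The rule in the protocol.** Protocol 9.5 leaves the same admissions out of the interim and "end-of-trial safety data analysis but will be documented in the patient notes". It does not say they are kept off the eCRF. The section begins: "The following will not require reporting although will be documented on the eCRF".

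**The other exempt group.** For venesection and biopsy events SAP 1.13.1 says: "The following will not require reporting although will be documented on the eCRF and will be included in the primary outcome".

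**Closing sentences of SAP 1.13.1.** One says that "any hospitalisation that is not associated with the IMP will not be reported", apart from prolongation caused by the IMP. The next says: "Unscheduled and/or emergency hospitalisations that are not expected due to the natural course of the disease will be reported". AEs are reviewed at each visit from the patient's "report as well as documentation from medical notes".

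**The concern.** The outcome definition and the counting rule do not match. A reader of Table 6 would take the SAE row as all serious events in treated patients, because nothing in SAP 1.12.1, SAP 2.5 or the table notes says otherwise. Under SAP 1.13.1 a class of admissions, some of which would meet the SAE definition, is removed before data entry.

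This matters because the trial has one open-label group and no hypothesis tests, so the primary objective is answered by these counts and listings alone. The removal depends on an unblinded judgement that an admission was due to the disease. If the admission is never entered, that judgement can be checked only in the patient notes, not in the trial database. Table 7 already has a causality grade for events unlikely to be related to the IMP, which suggests that unrelated events were meant to be listed and graded rather than left out.

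**Working it through.** **1. The plan's own figure.** SAP 1.14 gives 0% to 31% for no adverse reactions in 10 patients. The two-sided exact upper limit is 1 − 0.025^(1/10) = 0.3085, or 31%. The figure reproduces. It concerns adverse reactions, so the hospitalisation rule does not alter it.

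**2. Direction of the effect.** Let S be the number of SAEs under SAP 1.13. Let H be those among them whose admission is judged expected from disease progression, and E the part of H still entered as serious by another route, such as the notes review. The tabulated count is T = S − (H − E), with 0 ≤ E ≤ H. So T ≤ S, with equality when H = 0 or E = H. The patient count falls by one for each patient whose only SAEs are omitted ones.

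**3. Can an exempt admission be an SAE?** Only if it was for an untoward event. By my classification the list in SAP 1.13.1 has 29 named items:
- 11 are care only (for example transfusions, IV iron, hydrotherapy);
- 5 are worded as existing EB disease (for example pain from ongoing wounds);
- 3 mix an event with care (for example dental extraction or abscess);
- 10 name only an untoward event (for example fractures, eye infections, de-gloving injury).

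11 + 5 + 3 + 10 = 29. So 10 items (strict) to 10 + 3 + 5 = 18 (wide) could describe an SAE if admission was required. These are kinds of event, not expected numbers. The condition that the admission be expected from disease progression governs the whole list, so a listed event outside that condition is not exempt.

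**4. Does exemption from reporting imply exclusion from analysis?** Not in this SAP. The venesection and biopsy group, which includes biopsy-site infection needing oral antibiotics as well as mild bruising, is exempt from reporting but is entered and analysed. Within SAP 1.13.1 only the hospitalisations are expressly taken out.

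**5. SAP against protocol.** Both exclude the admissions from the two analyses. Only the SAP says they are not entered. The opening sentence of protocol 9.5 may imply entry, but the hospitalisation sentence there mentions only the patient notes, so this difference is implied rather than explicit.

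**6. The two closing sentences.** Take an emergency admission unrelated to the IMP and not expected from EB. The first sentence says it is not reported; the second says it is. Both cannot hold.

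**7. What an omission would do.** The documents give no admission rate, so no shortfall can be calculated. As an assumption for illustration, suppose Table 6 showed no patient with an SAE and k patients had been omitted. The plan does not call for these intervals; they show only how much one patient matters at this sample size.

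| k omitted | N = 10, exact 95% interval | N = 5, exact 95% interval |
|---|---|---|
| 0 | 0 to 30.8% | 0 to 52.2% |
| 1 | 0.3 to 44.5% | 0.5 to 71.6% |
| 2 | 2.5 to 55.6% | 5.3 to 85.3% |
| 3 | 6.7 to 65.2% | 14.7 to 94.7% |

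**The case against.** The strongest reply is that this is a prespecified operational rule, stated in both documents, and that a specific rule overrides a general regulatory definition. SAP 2.5 opens by referring to events as the protocol specifies them. Protocol 9.4 states that disease-progression deaths and outcome-measure events are not SAEs, so the plan's working concept is not purely all-cause.

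Part of this stands. The exclusion from analysis is disclosed in advance and is not an invention of the SAP. But the reference to the protocol in SAP 2.5 sits in the sentence on reporting to the data monitoring committee; the sentences on totals and listings carry no such limit. Protocol 9.4 does not mention hospitalisations and keeps the events it covers on the CRF. Prespecifying an exclusion does not reconcile it with an outcome definition that omits it.

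A second reply is that little is lost. The notes are reviewed at each visit and Table 7 records seriousness, so the underlying event may be entered as a serious AE. IMP-associated admissions and unexpected unscheduled ones remain reportable. Examination and photography continue at every visit, the committee monitors AEs, and monitors have access to source records. This stands as a limit on size. It does not remove the point, because the plan does not say whether the underlying event of an exempt admission is entered or marked serious.

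**Conclusion.** The inconsistency is real and should be fixed. As written, the tabulated SAE count can only equal or fall below the count that SAP 1.12.1 and 1.13 define. The size is unknown. In patients it lies between 0 and the number treated (5 to 10), and it is 0 if no such admission occurs or if every underlying event is entered as serious. The conclusion rests on reading the SAE definition as all-cause, which follows from the AE definition, and on finding no passage that restores these admissions to the primary outcome.

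A reader might infer more than the documents support:
- **That the count will certainly be too low, or by a calculable amount.** There is no admission rate, and the notes review may capture the event.
- **That serious reactions to the IMP are hidden.** IMP-associated admissions stay reportable. SAR and SUSAR counts are touched only if such an admission is misjudged as disease, so AR, SAR and SUSAR counts are less affected.
- **That the stated precision is wrong.** The 0% to 31% interval is for adverse reactions and reproduces.
- **That the SAP departs from the protocol on the analysis.** It does not. What it adds is the explicit rule against eCRF entry.

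**What to change.** 1. In SAP 1.13.1 and protocol 9.5, limit the list to an exemption from expedited SAE reporting, and use the same eCRF wording in both.
2. Enter every hospitalisation from Day 0 on the eCRF with its reason, a planned/unplanned flag, an expected-EB flag and the Table 7 causality grade. Count as SAEs those due to an untoward event. Planned admissions are entered too, so that the planned/unplanned judgement can also be checked.
3. In Table 6 show all SAEs, split into pre-listed EB categories and other.
4. Reconcile the two closing sentences of SAP 1.13.1 on admissions not associated with the IMP, and the matching text in protocol 9.5.

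A footnote restricting Tables 6 and 7 would make the text consistent, but the attribution would still be uncheckable from the database. The fix does not blind the causality judgement; it makes it visible.

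The cost is wording in two sections, a few more eCRF entries for 5 to 10 patients, and two rows in Table 6. The downside is a possibly larger, less favourable SAE count; the split shows how much of it falls in pre-listed EB categories.
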